## 10.6. Appendix 6: Abbreviations

The following is a list of abbreviations that may be used in the protocol.

Abbreviation	Term
2019-nCoV	novel coronavirus 2019
ACIP	Advisory Committee on Immunization Practices
AE	adverse event
AESI	adverse event of special interest
ALT	alanine aminotransferase
AST	aspartate aminotransferase
β-hCG	beta-human chorionic gonadotropin
CBER	Center for Biologics Evaluation and Research
CDC	Centers for Disease Control and Prevention (United States)
CFR	Code of Federal Regulations
CI	confidence interval
CIOMS	Council for International Organizations of Medical Sciences
CK	creatine kinase
CONSORT	Consolidated Standards of Reporting Trials
COVID-19	coronavirus disease 2019
CRF	case report form
CRO	contract research organization
CRP	C-reactive protein
CSR	clinical study report
DILI	drug-induced liver injury
DMC	data monitoring committee
DNA	deoxyribonucleic acid
EC	ethics committee
ECG	electrocardiogram
eCRF	electronic case report form
e-diary	electronic diary
EDP	exposure during pregnancy
EMA	European Medicines Agency
ESR	erythrocyte sedimentation rate
EU	European Union
EUA	emergency use authorization
EudraCT	European Clinical Trials Database
FDA	Food and Drug Administration
FSH	follicle-stimulating hormone
GCP	Good Clinical Practice
GGT	gamma-glutamyl transferase
GMC	geometric mean concentration

Abbreviation	Term
GMFR	geometric mean fold rise
GMR	geometric mean ratio
HBV	hepatitis B virus
HCV	hepatitis C virus
HIPAA	Health Insurance Portability and Accountability Act
HIV	human immunodeficiency virus
HRT	hormone replacement therapy
IB	investigator's brochure
ICD	informed consent document
ICH	International Council for Harmonisation
ID	identification
IgG	immunoglobulin G
IL-6	interleukin-6
IMP	investigational medicinal product
IND	investigational new drug
INR	international normalized ratio
IP manual	investigational product manual
IPAL	Investigational Product Accountability Log
IRB	institutional review board
IRT	interactive response technology
ISF	investigator site file
IV	intravenous(ly)
IWR	interactive Web-based response
LDH	lactate dehydrogenase
LFT	liver function test
LLOQ	lower limit of quantitation
LNP	lipid nanoparticle
LS	least squares
MedDRA	Medical Dictionary for Regulatory Activities
MERS	Middle East respiratory syndrome
MIS-C	multisystem inflammatory syndrome in children
modRNA	nucleoside-modified messenger ribonucleic acid
N	SARS-CoV-2 nucleoprotein
N/A	not applicable
NAAT	nucleic acid amplification test
NIMP	noninvestigational medicinal product
P2 S	SARS-CoV-2 full-length, P2 mutant, prefusion spike glycoprotein
PCR	polymerase chain reaction
PI	principal investigator
PPE	personal protective equipment
PT	prothrombin time

Abbreviation	Term
RCDC	reverse cumulative distribution curve
RNA	ribonucleic acid
RSV	respiratory syncytial virus
RT-PCR	reverse transcription-polymerase chain reaction
S	spike protein
S1	spike protein S1 subunit
SAE	serious adverse event
SAP	statistical analysis plan
SARS	severe acute respiratory syndrome
SARS-CoV-2	severe acute respiratory syndrome coronavirus 2
SoA	schedule of activities
SOP	standard operating procedure
SRSD	single reference safety document
SSID	single subject identification
SUSAR	suspected unexpected serious adverse reaction
TBili	total bilirubin
Th 1	T-helper type 1
UK	United Kingdom
ULN	upper limit of normal
US	United States
VOC	variant of concern
WHO	World Health Organization
WOCBP	woman/women of childbearing potential

1. VERSION HISTORY

Table 1. Summary of Changes

Version/ Date	Associated Protocol Amendment	Rationale	Specific Changes
1/ 17 Feb 2021	1 26 Jan 2021	N/A	N/A
2/ 06 May 2021	2 03 May 2021	Protocol amendment 2 and BDR team review	
 1. Booster study-related information added. 2. Removed “S1-binding IgG” throughout the document, as “full-length S-binding IgG” assay is the chosen assay for this protocol. 3. “Equivalence” is replaced with “similarity” for statistical comparisons. 4. Removed “by day” e-diary figures.
3/ 15 Oct 2021	2 03 May 2021	CCI [REDACTED]	
 1. Revised Section 5.1.2 to sequentially evaluate the 3 primary objectives. 2. Revised Section 7 to indicate 2 separate analyses will be performed.

2. INTRODUCTION

This SAP provides the detailed methodology for summary and statistical analyses of the data collected in Study C4591017. This document may modify the plans outlined in the protocol; however, any major modifications of the primary endpoint definition or its analysis will also be reflected in a protocol amendment.

2.1. Study Objectives, Endpoints, and Estimands

The estimands corresponding to each primary and secondary objective are described in [Table 2.1](#) and [Table 2.2](#). The estimands to evaluate the immunogenicity objectives are based on evaluable populations (see [Section 4](#) for definition). These estimands estimate vaccine effect in the hypothetical setting where participants follow the study schedules and protocol requirements as directed. Missing serology results will not be imputed. Immunogenicity results that are below the LLOQ, denoted as BLQ, will be set to $0.5 \times \text{LLOQ}$ in the analysis; this may be adjusted once additional data on the assay characteristics become available.

In the primary safety objective evaluations, missing AE start dates will be imputed according to Pfizer safety rules ([Section 5.3](#)). No other missing information (eg, missing e-diary data) will be imputed in the safety analysis.

Primary Study

Table 2.1 Primary Study – List of Primary and Secondary Objectives, Endpoints, and Estimands

Primary Immunogenicity Objectives – Lot Comparisons	Estimands	Primary Immunogenicity Endpoints

 To demonstrate that the immune responses induced by BNT162b2 are similar across the 3 US lots (Arms 1, 2, and 3) in participants without evidence of SARS CoV-2 infection during the study. 	In participants complying with the key protocol criteria (evaluable participants): 
 GMR from one US lot to another lot (Arm 1/Arm 2, Arm 1/Arm 3, and Arm 2/Arm 3) 1 month after Dose 2 	
 Full-length S-binding IgG levels

 To demonstrate that the immune response induced by the EU lot (Arm 4) of BNT162b2 is similar to the pooled US lots (Arms 1, 2, and 3) in participants without evidence of SARS-CoV-2 infection during the study. 	In participants complying with the key protocol criteria (evaluable participants): 
 GMR from EU lot (Arm 4) to the pooled US lots (Arm 4/pooled Arms 1, 2, and 3) 1 month after Dose 2 	
 Full-length S-binding IgG levels
Primary Immunogenicity Objectives – Dose Comparison	Estimands	Primary Immunogenicity Endpoints

 To demonstrate the noninferiority of the immune response to prophylactic BNT162b2 in participants receiving 20 µg compared to participants receiving the standard 30-µg dose (prepared from the same manufacturing lot) without evidence of SARS-CoV-2 infection during the study. 	In participants complying with the key protocol criteria (evaluable participants): 
 GMR, estimated by the ratio of the geometric mean of SARS-CoV-2 neutralizing titers in the 2 dose groups 1 month after Dose 2 	
 SARS-CoV-2 neutralizing titers
Primary Safety Objectives	Estimands	Primary Safety Endpoints

 To evaluate the safety of BNT162b2 when administered on a 2-dose schedule in healthy participants 12 through 50 years of age. 	In participants receiving at least 1 dose of study intervention from each vaccine group (individual and pooled US lots, EU lot, 20-µg dose), the percentage of participants reporting: 
 Local reactions for up to 7 days following each dose Systemic events for up to 7 days following each dose AEs and SAEs from Dose 1 to 1 month after Dose 2 	
 Local reactions (pain at the injection site, redness, and swelling) Systemic events (fever, fatigue, headache, chills, vomiting, diarrhea, new or worsened muscle pain, and new or worsened joint pain) AEs SAEs

Table 2.1 Primary Study – List of Primary and Secondary Objectives, Endpoints, and Estimands

Secondary Immunogenicity Objectives	Estimands	Secondary Immunogenicity Endpoints

 To describe the immune responses induced by different 30-µg dose manufacturing lots of BNT162b2. 	In evaluable participants from each vaccine group (individual and pooled US lots, EU lot): 
 GMCs at baseline (before Dose 1) and 1 month after Dose 2 GMFR from baseline (before Dose 1) to 1 month after Dose 2 	
 Full-length S-binding IgG levels

 To describe the immune responses induced by different doses of BNT162b2. 	In evaluable participants from each vaccine group (20 µg and 30 µg from the same US lot): 
 GMTs at baseline (before Dose 1) and 1 month after Dose 2 GMFR from baseline (before Dose 1) to 1 month after Dose 2 	
 SARS-CoV-2 neutralizing titers

Note: “US lots” refers to lots of study vaccine containing drug substance manufactured in the United States. “EU lot” refers to the lot of study vaccine containing drug substance manufactured in Europe.

Booster Study

Table 2.2 Booster Study – List of Primary Objectives, Endpoints, and Estimands

Primary Immunogenicity Objectives	Estimands	Primary Immunogenicity Endpoints

 To describe the immune responses induced by a third dose of study intervention (either BNT162b2 30 µg or BNT162b2.B.1.351* 30 µg). 	In evaluable participants from each vaccine group (either BNT162b2 30 µg or BNT162b2.B.1.351 30 µg): 
 Geometric mean neutralizing titers at baseline (before Dose 1), 1 month after Dose 2, before Dose 3, and 1 week after and 1 month after Dose 3 Geometric mean IgG concentrations at baseline (before Dose 1), 1 month after Dose 2, before Dose 3, and 1 week after and 1 month after Dose 3 GMFRs from 1 month after Dose 2 to 1 week after and 1 month after Dose 3 and from before Dose 3 to 1 week after and 1 month after Dose 3 The percentages of participants with seroresponse[§] (based on neutralizing titers) to the reference strain at 1 	
 SARS-CoV-2 reference-strain neutralizing titer[†] SARS-CoV-2 B.1.351-strain neutralizing titer^{††} Full-length S-binding IgG levels

Table 2.2 Booster Study – List of Primary Objectives, Endpoints, and Estimands

Primary Immunogenicity Objectives	Estimands	Primary Immunogenicity Endpoints
	month after Dose 2, before Dose 3, and 1 week after and 1 month after Dose 3 
 The percentages of participants with seroresponse[§] (based on neutralizing titers) to the B.1.351 variant strain at 1 month after Dose 2, before Dose 3, and 1 week after and 1 month after Dose 3 	
Primary Safety Objectives	Estimands	Primary Safety Endpoints

 To evaluate the safety and tolerability profile of a third dose of study intervention (either BNT162b2 30 µg or BNT162b2.B.1.351* 30 µg) administered to participants (18 through 50 years of age) who received two 30-µg doses of BNT162b2, approximately 3 months after Dose 2. 	In participants receiving the third dose of study intervention, the percentage of participants reporting: 
 Local reactions for up to 7 days following the booster dose Systemic events for up to 7 days following the booster dose AEs and SAEs from the booster dose to 1 month after the booster dose. 	
 Local reactions (pain at the injection site, redness, and swelling) Systemic events (fever, fatigue, headache, chills, vomiting, diarrhea, new or worsened muscle pain, and new or worsened joint pain) AEs SAEs

* BNT162.B.1.351 = BNT162b2s01 vaccine encoding for the full-length spike protein of South African–origin variant B.1.351 (formerly BNT162b2_{SA}).

† SARS-CoV-2 reference-strain neutralizing titers = neutralizing titers against SARS-CoV-2 USA-WA1/2020 virus.

†† SARS-CoV-2 B.1.351-strain neutralizing titers = neutralizing titers against SARS-CoV-2 virus with B.1.351 spike.

§ Seroresponse is defined as ≥ 4 -fold increase from baseline (before Dose 1) to the specified time point. If the baseline measurement is below LLOQ, a postvaccination measurement of $\geq 4 \times$ LLOQ is considered a seroresponse.

2.2. Study Design

Primary Study

This is a Phase 3, randomized, observer-blind study to evaluate the safety, tolerability, and immunogenicity of 4 manufacturing lots of BNT162b2 as a 30-µg dose and an additional 20-µg dose arm using one of the same manufactured 30-µg lots. BNT162b2 is an RNA-based COVID-19 vaccine, administered on a 2-dose schedule in healthy participants 12 through 50 years of age. The study will be conducted in the United States.

Participants will be randomized to 1 of 5 arms in a 2:2:2:1:2 ratio (Arm 1: Arm 2: Arm 3: Arm 4: Arm 5), where Arms 1, 2, and 3 contain US-manufactured drug substance for 30-µg dosing; Arm 4 contains EU-manufactured drug substance for 30-µg dosing; and Arm 5 contains US-manufactured drug substance for 20-µg dosing. In order to allow for balanced age representation across all arms, the randomization will be stratified by age groups: 12 through 17, 18 through 30, and 31 through 50 years.

Approximately 340 participants will be randomly assigned to each of the 3 US lots (Arms 1-3) and to the 20-µg arm (Arm 5) and approximately 170 participants will be randomly assigned to the EU lot (Arm 4), for a total of approximately 1530 randomized participants. It is expected that approximately 1224 evaluable participants will complete the study, based on a 20% nonevaluable rate. The duration of the study for each participant will be approximately 2 months. This study is observer-blinded, as the volumes of the 20-µg and the 30-µg doses of investigational vaccine are different.

Participants will receive 1 dose of study intervention as randomized at each vaccination visit (Visits 1 and 2) separated by 21 days.

Blood samples will be collected at Visit 1 (Day 1/Vaccination 1) and Visit 3 (1 month after Dose 2) to assess immunogenicity; during the same visits, blood and nasal swab samples will be collected to detect past or current SARS-CoV-2 infection, respectively. Participants will be observed for 30 minutes after each vaccination and any reactions occurring during that time will be recorded as AEs. Local reactions, systemic events (including fever), and use of antipyretic medication occurring within 7 days after each vaccination will be collected via a provided e-diary (or e-diary application). AEs and SAEs will be collected from the signing of informed consent through and including Visit 3 (1 month after Dose 2). In addition, any AEs occurring up to 48 hours after the blood draw and nasal swab collection at Visit 3 must be recorded in the CRF.

Booster Study

Protocol amendment 2 added a booster study in which a subset of the adult participants (18 through 50 years of age) who each received two 30-µg doses of the designated US lot(s) will be randomly assigned to 1 of 2 arms in a 1:1 ratio as shown:

Arm Name	Study Intervention
Booster 1	BNT162b2 30 µg
Booster 2	BNT162b2.B.1.351 30 µg

Approximately 30 participants will be assigned to each arm for a total of 60 participants enrolled. It is expected that approximately 48 evaluable participants will complete the study, based on a 20% nonevaluable rate. The duration of the study for each participant will be approximately 1 month. This study is observer-blinded, to minimize changes in study conduct compared with the primary study.

Participants will receive a third dose of study intervention as randomized at Visit 4, 3 months after the receipt of Dose 2.

Blood samples will be collected at Visit 4 (Vaccination 3), Visit 5 (1 week after Dose 3), and Visit 6 (1 month after Dose 3) to assess immunogenicity; during the same visits, except Visit 5, blood and nasal swab samples will be collected to detect past or current SARS-CoV-2 infection, respectively. Participants will be observed for 30 minutes after the booster vaccination and any reactions occurring during that time will be recorded as AEs. Local reactions, systemic events (including fever), and use of antipyretic medication occurring within 7 days after the booster vaccination will be collected via a provided e-diary (or e-diary application). AEs and SAEs will be collected from Visit 4 through and including Visit 6 (1 month after Dose 3). In addition, any AEs occurring up to 48 hours after the blood draw and nasal swab collection at Visit 6 must be recorded in the CRF.

3. ENDPOINTS AND BASELINE VARIABLES: DEFINITIONS AND CONVENTIONS

3.1. Primary Endpoints

3.1.1. Primary Study – Primary Immunogenicity Endpoints – Lot Comparisons

- Full-length S-binding IgG levels at 1 month after Dose 2 for participants receiving vaccine from the US lots (Arms 1, 2, and 3)
- Full-length S-binding IgG levels at 1 month after Dose 2 for participants receiving vaccine from the EU lot (Arm 4) and the 3 pooled US lots (pooled Arms 1, 2, and 3)

Concentrations of IgG levels will be determined in all participants at Visit 1 (Day 1) and Visit 3 (1 month after Dose 2) using the SARS-CoV-2 full-length S-binding IgG-level assay.

Values below the LLOQ will be set to $0.5 \times \text{LLOQ}$ for the analysis. The LLOQ value for full-length S-binding IgG will be included in the analysis specification once it is available.

3.1.2. Primary Study – Primary Immunogenicity Endpoint – Dose Comparison

- SARS-CoV-2 neutralizing titers at 1 month after Dose 2 for participants receiving 30- μg or 20- μg doses (prepared from the same manufacturing lot)

Titers will be determined in all participants at Visit 1 (Day 1) and Visit 3 (1 month after Dose 2) using the SARS-CoV-2 neutralizing assay.

Values below the LLOQ will be set to $0.5 \times \text{LLOQ}$ for the analysis. The LLOQ value for neutralizing titers will be included in the analysis specification once it is available.

3.1.3. Booster Study – Primary Immunogenicity Endpoints

- SARS-CoV-2 reference-strain neutralizing titers and SARS-CoV-2 B.1.351-strain neutralizing titers at each time point for participants receiving a third dose of BNT162b2 30 µg or BNT162b2.B.1.351 30 µg
- Fold rises in SARS-CoV-2 reference-strain neutralizing titers and SARS-CoV-2 B.1.351-strain neutralizing titers for participants receiving a third dose of BNT162b2 30 µg or BNT162b2.B.1.351 30 µg
- Seroresponse (≥ 4 -fold increase from baseline) (based on neutralizing titers) to the SARS-CoV-2 reference strain and to the SARS-CoV-2 B.1.351 variant strain.
- Full-length S-binding IgG levels at each time point for participants receiving a third dose of BNT162b2 30 µg or BNT162b2.B.1.351 30 µg
- Fold rises in full-length S-binding IgG levels for participants receiving a third dose of BNT162b2 30 µg or BNT162b2.B.1.351 30 µg

Titers will be determined in all participants of the booster study at Visit 1 (Day 1), Visit 3 (1 month after Dose 2), Visit 4 (before Dose 3), Visit 5 (1 week after Dose 3), and Visit 6 (1 month after Dose 3) using the SARS-CoV-2 reference-strain and the SARS-CoV-2 B.1.351-strain neutralizing assays.

Concentrations of IgG levels will be determined in all participants of the booster study at Visit 1 (Day 1), Visit 3 (1 month after Dose 2), Visit 4 (before Dose 3), Visit 5 (1 week after Dose 3), and Visit 6 (1 month after Dose 3) using the SARS-CoV-2 full-length S-binding IgG-level assay.

Fold rises will be calculated for each participant of the booster study by taking the ratio of titers or IgG concentrations from a later time point to an earlier time point.

Seroresponse is defined as ≥ 4 -fold increase from baseline (before Dose 1) to the specified time point. If the baseline measurement is below LLOQ, a postvaccination measurement of $\geq 4 \times$ LLOQ is considered a seroresponse.

Values below the LLOQ for both full-length S-binding IgG and neutralizing titers will be set to $0.5 \times$ LLOQ for the analysis. The LLOQ values for both will be included in the analysis specification once they are available.

3.1.4. Primary Safety Endpoints

The primary study and booster study have similar safety endpoints as follows:

- Local reactions (pain at the injection site, redness, and swelling) within 7 days after each dose

- Systemic events (fever, fatigue, headache, chills, vomiting, diarrhea, new or worsened muscle pain, and new or worsened joint pain) within 7 days after each dose
- AEs and SAEs from Dose 1 to 1 month after Dose 2 for participants in the primary study and from Dose 3 to 1 month after Dose 3 for participants in the booster study

3.1.4.1. Local Reactions

The local reactions assessed and reported in the e-diary are pain at the injection site, redness, and swelling, from Day 1 through Day 7 after each dose, where Day 1 is the day of each dose. This section describes derivations with details for the assessment of local reactions: presence, severity level, duration, and onset day.

Presence or Absence

For each local reaction and any local reaction on any day, Table 3 defines the algorithm to derive the presence of a reaction (yes or no) during the interval from Day 1 through Day 7, where Day 1 is the day of each dose.

Table 3. Derived Variables for Presence of Each and Any Local Reaction Within 7 Days for Each Dose

Variable	Yes (1)	No (0)
Presence of each local reaction on any day	Participant reports the reaction as “yes” on any day (Day 1 through Day 7).	Participant reports the reaction as “no” on all 7 days (Day 1 through Day 7) or as a combination of “no” and missing on all 7 days (Day 1 through Day 7).
Presence of any local reaction on any day	Participant reports any local reaction as “yes” on any day (Day 1 through Day 7).	For all 3 local reactions, participant reports “no” on all 7 days (Day 1 through Day 7) or a combination of “no” and missing on all 7 days (Day 1 through Day 7).

Note: Missing e-diary data will not be imputed. Participants with no e-diary data reported will not be included in the e-diary summaries.

Severity and Maximum Severity

Redness and swelling will be measured and recorded in measuring device units (range: 1 to 21) and then categorized during analysis as absent, mild, moderate, or severe based on the grading scale in [Table 4](#). Measuring device units can be converted to centimeters according to the following scale: 1 measuring device unit = 0.5 cm. Pain at the injection site will be assessed by the participant as mild, moderate, or severe according to the grading scale in [Table 4](#).

If a Grade 3 local reaction is reported in the reactogenicity e-diary, a telephone contact should occur to ascertain further details and determine whether a site visit is clinically indicated. Only an investigator or medically qualified person is able to classify a participant's local reaction as Grade 4. If a participant experiences a confirmed Grade 4 local reaction, the investigator must immediately notify Pfizer and, if it is determined to be related to the administration of the study intervention, further vaccinations will be discontinued in that participant.

Table 4. Grading Scales for Local Reactions

Local Reaction	Mild (Grade 1)	Moderate (Grade 2)	Severe (Grade 3)	Potentially Life Threatening (Grade 4 ^a)
Pain at the injection site	Does not interfere with activity	Interferes with activity	Prevents daily activity	Emergency room visit or hospitalization for severe pain
Redness	>2.0 cm to 5.0 cm (5 to 10 measuring device units)	>5.0 cm to 10.0 cm (11 to 20 measuring device units)	>10 cm (≥ 21 measuring device units)	Necrosis or exfoliative dermatitis
Swelling	>2.0 cm to 5.0 cm (5 to 10 measuring device units)	>5.0 cm to 10.0 cm (11 to 20 measuring device units)	>10 cm (≥ 21 measuring device units)	Necrosis

- a. Only an investigator or medically qualified person is able to classify a reaction as Grade 4; therefore, a confirmed Grade 4 should be reported as an AE in the case report form.

For each local reaction after each dose, the maximum severity grade will be derived for the e-diary collection period (Day 1 through Day 7, where Day 1 is the day of each dose) as follows:

maximum severity grade = highest grade (maximum severity) within 7 days after vaccination (Day 1 through Day 7) among the severity grades reported for that local reaction in the e-diary.

Duration (First to Last Day Reported)

The duration (days) of each local reaction will be calculated as the number of days from the start of the first reported reaction to the resolution of the last reported reaction, inclusive. Resolution is defined as the last day on which the reaction is recorded in the e-diary if the reaction lasted 7 days or less, or the day the reaction ended if it continued beyond Day 7 (the latter will be collected on the CRF). If there is no known date when the reaction ended, then duration will be missing (unknown). However, if a reaction is ongoing at the time of a subsequent dose, the end date/day for the ongoing event would be the date/day that the next dose is administered, which will be used for the duration computation. Participants with no reported reaction have no duration.

Onset Day

The onset day of each local reaction will be derived. Onset day is defined as the first day of reporting the reaction with any severity after vaccination.

For the onset day of each local reaction, if participants report a change in severity of the local reaction, only the first day of reporting that specific local reaction will be counted.

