6.1.2.1.2. Supplementary Analyses

As supplementary analyses to support the assessment of local reactions, the following endpoints (as defined in [Section 3.1.4.1](#)) will be summarized with the same analysis time point and analysis population:

- Duration (days) of each local reaction after each dose.
- Onset day of each local reaction after each dose.

These continuous endpoints will be summarized by displaying n, mean, median, standard deviation, minimum, and maximum for each vaccine group and the pooled US lots for the primary study and by vaccine group for the booster study.

In addition, the proportions of participants reporting each prompted local reaction after any dose will be summarized by maximum severity level for the primary study.

Figures:

Bar charts with the proportions of participants for each local reaction throughout 7 days will be plotted for each dose by vaccine group and the pooled US lots for the primary study and by vaccine group for the booster study. The bars will be divided into severity categories to highlight the proportions of participants by maximum severity.

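### Does the SAP's duration summary let in redness and swelling too small to be graded, so that its n cannot be reconciled with the severity table?

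*SAP*

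**What the plan says.** SAP 3.1.4.1 (Severity and Maximum Severity) says: "Redness and swelling will be measured and recorded in measuring device units (range: 1 to 21) and then categorized during analysis as absent, mild", then moderate and severe, with 1 unit equal to 0.5 cm. In SAP Table 4 the Grade 1 band for both reactions is ">2.0 cm to 5.0 cm (5 to 10 measuring device units"). Protocol 8.2.2.2 and its Table 1 use the same conversion and the same Grade 1 band.

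Under Duration, the length of a reaction is the "number of days from the start of the first reported reaction to the resolution of the last reported reaction, inclusive". It ends on the last diary day on which the reaction is recorded, or on "the day the reaction ended if it continued beyond Day 7 (the latter will be collected on the CRF"). A duration with no known end date is set to missing. The section adds: "Participants with no reported reaction have no duration".

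Under Onset Day: "Onset day is defined as the first day of reporting the reaction with any severity after vaccination". The sentence after it says that, when severity changes, only the first day of reporting counts.

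Table 3 defines presence by a participant's yes on any of Days 1 to 7. It gives no size threshold and does not refer to Table 4.

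The main table (SAP 6.1.2.1.1) is by maximum severity and cumulative across severity levels. Duration and onset are supplementary (SAP 6.1.2.1.2). They "will be summarized with the same analysis time point and analysis population", and "These continuous endpoints will be summarized by displaying n, mean, median, standard deviation, minimum, and maximum for each vaccine group".

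**The concern.** The severity table and the duration summary appear to use different entry rules. The first needs a graded size. The second asks only that a reaction was reported. The SAP allows for sub-threshold readings, because the recording range starts at 1 unit and absent is one of the categories given to recorded values. By contrast, SAP 3.1.4.2 gives fever, the other measured event, an explicit cut-off of 38.0°C, and redness and swelling have no equivalent statement of what counts as a reaction.

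If the literal reading were programmed, the duration n for redness or swelling could exceed the cumulative severity count for the same dose, arm and population, and a reader could not reconcile the two. Few participants have these reactions, so a handful of small, short-lived readings could also shift the mean duration.

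**Working it through.** **1. Grade bands.** Inputs: 1 unit = 0.5 cm and the Table 4 cut-offs in cm (SAP 3.1.4.1).

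| Units | cm (units × 0.5) | Category |
|---|---|---|
| 1–4 | 0.5–2.0 | absent (not above 2.0 cm) |
| 5–10 | 2.5–5.0 | mild |
| 11–20 | 5.5–10.0 | moderate |
| 21 | 10.5 | severe |

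This reproduces the SAP's unit bands. Readings of 1 to 4 units have no grade.

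**2. The literal duration rule against a graded rule.** Made-up 7-day diaries in device units, with 0 for nothing recorded:

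| Diary | Maximum severity | Duration, any reading | Duration, 5 units or more | First day at 5 units or more |
|---|---|---|---|---|
| 2,3,2,0,0,0,0 | absent | 3 days | none | none |
| 3,6,6,4,2,0,0 | mild | 5 days | 2 days | Day 2 |
| 6,8,6,0,0,0,0 | mild | 3 days | 3 days | Day 1 |

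The first diary shows the mismatch: a duration without a grade. The second shows that ungraded days can also lengthen the duration of a participant who is graded.

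**3. Does the SAP force the literal reading?** No.
- Recorded values are categorized for analysis, and absent is one of the categories. A value categorized as absent is naturally read as no reaction, and the sentence denying a duration to participants without a reported reaction then excludes it.
- The maximum-severity rule in the same section treats grades as what is reported in the diary, so the SAP itself links reporting to grading.
- The onset wording can mean graded at any level, or regardless of severity. On the second meaning onset and duration share one entry rule, so a gap between those two n's is not established.

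**4. Would the two n's otherwise agree?** Not necessarily. An unknown end date makes the duration missing, so the duration n can already fall below the severity count by design.

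**5. Illustrative size.** Anchor: the 10.5% swelling rate in Protocol 2.3, taken as the graded rate. This is an assumption, since it comes from another study with a different age range and is not stated to be per dose. Graded count in an arm of 340: 340 × 0.105 = 35.7. Let p be the assumed further proportion of the arm reporting only 1 to 4 units. Duration n = 340 × (0.105 + p), and the sub-threshold share = p / (0.105 + p).

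| p | Duration n | Share | Fall in mean if these are 1 day shorter | If 2 days shorter |
|---|---|---|---|---|
| 0 | 35.7 | 0% | 0 | 0 |
| 1% | 39.1 | 8.7% | 0.09 days | 0.17 days |
| 2% | 42.5 | 16.0% | 0.16 days | 0.32 days |
| 5% | 52.7 | 32.3% | 0.32 days | 0.65 days |

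In a booster arm of 30 the graded count is 30 × 0.105 = 3.15, about 3; one sub-threshold reporter would be 1/(3 + 1) = 25% of the duration n. These falls leave out the opposite effect in step 2, where ungraded days lengthen graded durations, so the net direction is unknown.

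**The case for a change.** The best case for a change is that two programmers could both follow the SAP and produce different n's, and that removing such choices is what a SAP is for. Nothing in either document defines a reported redness or swelling as 5 units or more. Duration is a named output that displays n on the same population as the main table, so a reader would expect agreement. One sentence would settle it and needs no new data.

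Much of this stands: the definition is unstated, and the literal reading does admit ungraded readings. What does not stand is that the SAP directs analysts to include them, or that the result would mislead on anything that is decided from these tables.

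The obvious repair also needs care. If a grade were required for presence and onset, and for entry to the duration summary, while duration still ran from the first reading of any size, the diary 3,6,6,4,2,0,0 would have onset on Day 2 and a 5-day duration starting on Day 1. That would replace one inconsistency with another. It would also not make the n's match, because unknown end dates would still lower the duration n.

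**Conclusion.** This is a gap in definition that an analyst can fill sensibly from the same section: a reading categorized as absent is no reaction, and no reaction has no duration. No change to the plan follows.

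The number of participants affected cannot be derived from the documents and may be zero; it depends on what the e-diary lets participants enter, which is not described. Under an assumed 0% to 5% of an arm, the duration n in an arm of 340 would be about 36 to 53 against 36 graded. That range rests on the assumed share and on 10.5% as the graded rate; the shifts in mean duration also rest on the assumed difference in days. All are illustrative.

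The outputs concerned are supplementary and descriptive, the same rule applies to every arm, and the main reactogenicity tables are already graded. For the Table 3 presence flags no planned output is named, so there the point is only a missing cross-reference to Table 4. The immunogenicity hypotheses are untouched.
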